1.0 OBJECTIVES

The overall objective is to determine whether the natural flaxseed lignan, secoisolariciresinol diglycoside (SDG), in amounts providing plasma lignan levels associated with reduced breast cancer risk, will favorably modulate risk biomarkers for breast cancer development. This will provide biologic evidence of SDG's potential for breast cancer chemoprevention. Based on a positive pilot study in which both Ki-67 and the proportion of women with atypical cytomorphology was reduced with 12 months of SDG 50 mg/day, a randomized, placebo-controlled clinical chemoprevention trial will be conducted wherein pre-menopausal women at increased risk for the development of breast cancer will receive Brevail® (200 mg, equivalent to 50 mg of SDG) or matched, blinded placebo for 12 months. A total of 242 subjects will be accrued, randomized 2:1 to SDG vs placebo, with the goal of achieving 220 subjects completing study and evaluable for biomarker change.

The primary objective is to determine if women randomized to 12 months of SDG exhibit greater change in the proportion of breast epithelial cells expressing the proliferation marker Ki-67/MIB-1 in hyperplastic benign breast tissue than do women randomized to placebo.

Secondary objectives are:

- 1) to determine if 12 months of SDG is associated with favorable modulation of other risk biomarkers including cytologic atypia, and serum levels of bioavailable estradiol and testosterone, IGF-I:IGFBP-3 ratio, c-peptide, adiponectin, and leptin.
- 2) to determine if Ki-67 and modulation of other risk biomarkers is correlated with change in blood or urine lignans.
- 3) to determine impact or potential impact on quality of life as measured by the BPQ breast pain questionnaire (a modified McGill Pain questionnaire), The Breast Cancer Prevention Trial (BCPT) Symptom Checklist a menstrual diary for cyclicity and cycle length for women not on cycle modulating contraceptives; and antimullerian hormone (AMH), a measure of follicular reserve.

An exploratory objective is to interrogate SDG's mechanism of action through measurement of changes in hormones, growth factors, gene expression, adipokines and cytokines and proteomic signatures.

The overriding hypothesis is that biomarkers assessed both in serum and in hyperplastic breast tissue obtained by RPFNA from high risk pre-menopausal women will be favorably modulated by 12 months of SDG without negatively affecting quality of life.

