Specifically, it is hypothesized that SDG administration will be associated with

- a reduction in proliferation as measured by Ki-67;
- a reduction in proportion of specimens with cytologic evidence of atypia;
- a favorable tolerability and quality of life profile;
- no significant impact on menstrual cycle length;
- no significant effect on follicular reserves as measured by early follicular phase anti-mullerian hormone in women entering the study between ages 21-35;
- a reduction in breast pain in those women entering the study with mastalgia.

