2.4.4.5 Adverse events

The main expected AEs from SDG were diarrhea, flatulence, and irregular menses. GI symptoms, usually grade 1, were encountered in 42%, irregular menses in 26%, and hot flashes in 6% of subjects. Only two grade 3 AEs were reported. One subject was diagnosed with DCIS on the basis of the mammogram performed prior to the 12 month RPFNA. This was not considered related to the study agent. One subject discontinued study after 3 months because of grade 3 pelvic pain that was thought to be possibly related to study agent

Frequency of adverse events by worst reported per subject.

Number	CTC Grade					
	0	1	2	3	4 or 5	Total
Total	7 (14%)	17 (35%)	23 (47%)	2 (4%)	0 (0%)	49

Change in plasma lignans did not correlate with change in Ki-67, adverse events (AEs), or compliance [101].

[figure not shown]

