11.2 Statistical Analysis

All analyses will be intent-to-treat. All subjects randomized will be evaluable for safety and all subjects that have both a pre and post specimen are evaluable for efficacy. Primary analysis of efficacy will be performed on all evaluable subjects and secondary analysis will be done on those subjects who received at least 6 months of study medication and were confirmed as being in the follicular phase for both RPFNA procedures. From our experience we have very little missing data; however, if the missing data rate is above 5%, we will use multiple imputation to impute these values to perform the primary and secondary analyses.

The primary outcome will be change in Ki-67 (percent of cells expressing Ki-67) from baseline to 12 months. The two-sample t-test will be used to compare the change in Ki-67 between the SDG

and placebo groups. Any difference in baseline values of Ki-67 between the two groups would be due to chance, however, if there is a significant difference, then analysis of covariance adjusting for baseline values will be performed. Due to potential skewness in these variables we will assess whether or not the Central Limit Theorem may be assumed. Given the sample size the existence of an extremely high degree of skewness would require the use of the Wilcoxon Signed Rank test.

For the secondary endpoints, similar methods as above will be used to compare the treatment and control groups at two time points for all markers, i.e., serum hormones and clinical laboratory tests. We will also correlate change in the primary biomarker Ki-67 with change in other markers (e.g., bioavailable estradiol, cytokines, RTqPCR results) using Pearson's correlation coefficient. Again, if there exists a high degree of skewness in these variables, Spearman's correlation will be utilized.

Multiple regression analysis will also be used to investigate whether changes in Ki-67 are due to variables other than treatment effect (e.g., age, cytromorphology, Gail risk; as well as the predictive effect of other biomarkers on modulation of Ki-67). Best subsets and stepwise approaches will be employed while controlling for treatment group.

For comparison of moderate or worse toxicities we will consider grade 3 toxicity or premature trial discontinuation as the critical events. The prevalence of events in the SDG vs. the placebo arm will be examined by Fisher's exact test.

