Evaluation of agent-induced hormonal changes - We will examine whether SDG has any effects on serum levels of bioavailable estradiol, and testosterone, determined at baseline and after 12 months of study medication. We will determine whether addition of SDG alters the frequency or length of menstrual cycles. Effects on follicular reserve will be evaluated with anti-mullerian hormone in a sub-cohort of pre-menopausal women between ages 21 and 35 at study entry. Antimullerian hormone (AMH) is one of the earliest and most sensitive measures of follicular reserve declines for approximately 10 years before the cessation of menses. A distinct advantage for trial purposes is that it does not vary with day of menstrual cycle [119].

Adverse Events and Quality of Life – Change from baseline to 12 months will be assessed for mastalgia (expected in 30-50% of subjects at baseline), menstrual cycle and follicular reserve, and quality of life, as a function of SDG intake, plasma lignan levels and urinary lignan excretion. We will use the breast pain questionnaire (BPQ), which is a modified short form of the McGill Pain questionnaire (SF-MPQ) to assess breast discomfort and the Breast Cancer Prevention Trials (BCPT) Symptom Checklist to monitor quality of life

Correlative analyses will be performed with plasma and urine ENL and total lignans as the independent variable, with modifying variables of baseline BMI age and specific SNPs such as CYP17.

Since this is a phase IIB trial, the power and sample size for the primary endpoint was determined with a two-sided type I error rate of 5%. All subsequent secondary, tertiary and exploratory analyses will also be tested with a two-sided type I error rate of 5%. This may result in an elevated false positive rate for these secondary and tertiary analyses, however, since this is a Phase IIB study, we felt to control the type I error rate for the secondary, tertiary and exploratory analyses would be too conservative.

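### The only planned between-arm test of CTCAE adverse events is cut at grade 3 or discontinuation, so it has low power for a shift in grade 0 to 2 symptoms; a comparison of worst grade should be added beside it

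*Combined protocol and SAP*

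**What the plan says.** Section 11.2 gives one between-arm test of toxicity, which it introduces as a comparison of toxicities that are moderate or worse: "we will consider grade 3 toxicity or premature trial discontinuation as the critical events". It continues: "The prevalence of events in the SDG vs. the placebo arm will be examined by Fisher's exact test". The safety set is broad ("All subjects randomized will be evaluable for safety"), and section 1.0 fixes its size: "A total of 242 subjects will be accrued, randomized 2:1 to SDG vs placebo". Multiplicity is left uncontrolled by design: "All subsequent secondary, tertiary and exploratory analyses will also be tested with a two-sided type I error rate of 5" percent.

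Section 8.2.2 lists severity grade among the data recorded for each event. Section 8.2.3 uses CTCAE version 4.0 and, for events without a CTCAE term, labels grade 2 moderate and grade 3 severe. The pilot report in 2.4.4.5 already tabulates worst grade per woman ("Frequency of adverse events by worst reported per subject"): 7 at grade 0, 17 at grade 1, 23 at grade 2, 2 at grade 3 and none higher, of 49.

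Section 1.0 lists "a favorable tolerability and quality of life profile" among the specific hypotheses. Section 11.2 also plans to assess change in mastalgia, menstrual cycle and quality of life using the BPQ, the menstrual diary and the BCPT checklist. It names no specific test for these.

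**The concern.** The adverse events seen with SDG in the pilot were mostly low grade: gastrointestinal symptoms, usually grade 1, in 42% of women and irregular menses in 26%. A test that starts at grade 3 cannot see a move from none to mild or from mild to moderate unless it leads to discontinuation. Tolerability is a stated hypothesis, and section 3.2 rests part of the case for SDG on it. The pilot had one arm, so this trial is the program's first randomized comparison of tolerability for this regimen. If the only formal test is insensitive where most events lie, a non-significant result says little either way.

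The cut also does not match its own description. A comparison of moderate or worse toxicity would, on the scale in 8.2.3, start at grade 2.

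**Working it through.** **The plan's own figures.** The documents state no power for the adverse-event test. The only stated power, 83% for Ki-67, reproduces: with 147 and 73 evaluable women, 2.5 / (6 × √(1/147 + 1/73)) = 2.91, which gives 83% by the normal approximation and 82.6% by the noncentral t.

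**Inputs.** 242 randomized 2:1 gives 161 SDG and 81 placebo; two-sided 5% (1.0, 11.2). The SDG worst-grade distribution is the pilot's: 7/49, 17/49, 23/49, 2/49. The share at grade 0 to 2 is (7 + 17 + 23)/49 = 95.9%. The placebo distribution is not in the documents. It is assumed to follow from SDG by dividing each cumulative odds by a common odds ratio (OR).

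**Placebo distribution at OR 2.**
- Grade ≥1: odds 42/7 = 6, halved to 3, so 75.0%.
- Grade ≥2: odds 25/24 = 1.042, halved to 0.521, so 34.2%.
- Grade 3: odds 2/47 = 0.0426, halved to 0.0213, so 2.1%.

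**Power.** Fisher power is by full enumeration. The tie-corrected rank-sum and the uncorrected chi-square are by simulation.

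| OR | Fisher, grade 3 | Fisher, grade ≥2 | Chi-square, grade ≥2 | Rank-sum, worst grade |
|---|---|---|---|---|
| 1 | 3% | 4% | 5% | 5% |
| 1.5 | 3% | 27% | 31% | 36% |
| 2 | 5% | 66% | 70% | 78% |
| 2.5 | 6% | 88% | 90% | 95% |

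At OR 2, moving the cut from grade 3 to grade 2 adds about 61 points, and using the full scale adds a further 12. Over ORs 1.5 to 2.5 the full scale adds about 7 to 12 points over Fisher at grade 2. Against the chi-square, which is less conservative than Fisher, it adds about 5 to 8.

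**The composite actually planned, dropout unrelated to arm.** Take 10% dropout in both arms (the rate assumed in 3.0), independent of grade 3, with grade 3 odds doubled:
- SDG: 1 − 0.90 × (1 − 0.0408) = 13.7%.
- Placebo: 1 − 0.90 × (1 − 0.0208) = 11.9%.
- Fisher power: 5%.

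**The composite, whole event doubling.** Four of 49 pilot women did not complete or were not evaluable. One of the two grade 3 women discontinued, and the other's completion status is not stated. If all four count as discontinuations, the pilot rate is 4/49 to 5/49, or 8.2% to 10.2%.

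| SDG | Placebo | Fisher power |
|---|---|---|
| 8.2% | 4.1% | 16% |
| 10.2% | 5.1% | 21% |
| 16.3% | 8.2% | 39% |
| 20.4% | 10.2% | 49% |

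**Other shapes of effect.**
- Grade 3 about 4% in both arms, placebo assumed at 30/35/31/4%: Fisher at grade 3 has 3% power, rank-sum about 80%.
- Grades 0 and 1 as in the pilot in both arms, grade 3 at 12% on SDG and 2% on placebo, with grade 2 taking up the difference: Fisher at grade 3 has about 80%, rank-sum about 10%.

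Neither test dominates. They detect different kinds of harm.

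**The case against.** A threshold for critical events is a defensible choice in a phase II trial powered on Ki-67, and four points against a stronger reading stand.

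1. A reader might infer that the test has almost no power on tolerability and that non-significance is nearly certain. The documents do not support that. Discontinuation at any grade counts, and under 5.9 a recurrent agent-related grade 2 event, with stated exceptions, leads to permanent stopping of the agent. If poor tolerability shows itself through discontinuation, a doubling has 16% to 49% power: low, but not negligible.
2. A reader might credit the whole gain to ordinal scoring. Most of it comes from using grades below 3, and a grade 2 cut captures most of that.
3. A reader might conclude that the Fisher test should be demoted. The last scenario above shows the cost: a rank-sum test would largely miss an excess confined to grade 3.
4. Low-grade symptoms are not ignored altogether, since the BPQ, BCPT checklist and menstrual diary capture some of them.

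The fourth point does not close the gap. These are not CTCAE grades, and the documents do not say that they cover the gastrointestinal events. The BCPT checklist asks about the past four weeks (Appendix 1, 8.1) and is given only at baseline and 12 months (6.1).

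It is also fair that worst grade pools unrelated all-cause events. In the pilot 42 of 49 women (86%) had at least one. Nothing in the plan says that a non-significant result will be read as good tolerability, and that caution would apply to a rank-sum test too.

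**Conclusion.** The concern holds in a limited form. The only planned between-arm CTCAE analysis discards the distinctions among grades 0, 1 and 2 except through discontinuation, and its cut does not match its label. Its power for a shift in low-grade symptoms is low: about 5% at a common odds ratio of 2 if dropout is unrelated to arm, and about 16% to 49% if the whole composite doubles from 4-10% on placebo. On the same odds-ratio assumption a rank-sum test has about 78% and a grade 2 cut about 66%.

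These figures rest on the pilot grade distribution carrying over to the SDG arm and on an assumed placebo distribution. No single power figure can be fixed from the documents. The findings support adding an analysis, not replacing the one planned.

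**What to change.** In section 11.2:

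- Add a between-arm comparison of worst post-randomisation CTCAE grade per woman, by Wilcoxon rank-sum or by a proportional-odds model stratified by oral-contraceptive use. Report the common odds ratio with its 95% CI.
- Show the table of worst grade by arm beside it.
- Keep the Fisher test as a planned comparison, not as a descriptive supplement, and bring its label into line with the grade labels in 8.2.3.
- Also report discontinuations separately by arm, so that a reader can see which part of the composite drives any difference.

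The cost is SAP wording and one further analysis of data already collected, with no extra women, visits or assays. There are two downsides. It adds one more unadjusted secondary test, which 11.2 already accepts in principle. And worst grade mixes unrelated events, so a common odds ratio should be read with the grade table.

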2.4.3 Eligibility criteria for SDG pilot study

Eligibility criteria included regular menstrual cycles, no oral contraceptives, a 3-fold or greater increase in 5-year estimated risk for breast cancer relative to SEER statistics for age group, and normal mammogram performed in the follicular phase of the menstrual cycle within 3 months of baseline RPFNA. Subjects on oral contraceptives were excluded in order to reduce subject hormonal heterogeneity and because it might be more difficult to demonstrate biomarker modulation from SDG in the face of exogenous hormones. Baseline RPFNA was also to be performed in the follicular phase and had to show unequivocal hyperplasia +/- atypia as well as a minimum Ki-67 expression of 2% in hyperplastic ducts. The Ki-67 value of 2% was chosen since this is the median Ki-67 value in hyperplastic tissue obtained by RPFNA from high risk pre-menopausal women in the follicular phase of the cycle [86]. Further, a Mayo Clinic series suggests that women having a biopsy showing atypical hyperplasia and a Ki-67 of 2% or higher have a significantly higher 10-year risk of breast cancer (14% versus 3%) [88]. The early-mid follicular phase is utilized due to greater subject comfort and less bleeding during RPFNA.

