11.1 Sample Size and Power

The primary outcome of interest is efficacy of SDG relative to the placebo, thus the pre- to post-treatment change in a proliferation index (percent of cells expressing Ki-67) is the basis of the power analyses. From our pilot study, the average percentage of cells expressing Ki-67 at baseline was 4%, and the average change in percent of cells expressing Ki-67 was a 2.4% reduction, for subjects meeting similar eligibility requirements as used in this trial.

A 2:1 randomization of 220 evaluable subjects will provide 83% power to detect a 2.5% reduction in Ki-67 for the treatment group compared to no reduction in the control group; this will be our primary endpoint. This is based on an assumption of a common standard deviation of 6% for change in Ki-67 in both groups and a Type I error rate of 5%. Within the target of 220 evaluable subjects, we expect to recruit 72 women taking oral contraceptives (OC) and 148 women not taking OCs. Because the efficacy of SDG is unknown for OC users, we considered different scenarios and evaluated the average effect in the SDG arm and the corresponding power. For 0-70% efficacy of SDG among OC users, the respective average Ki-67 reduction range from 1.7% to 2.3% will result in a statistical power ranging from 50% to 76%.

Ki-67 reduction in SDG arm (non-OC)	Efficacy of SDG in OC	Ki-67 reduction in SDG arm (OC)	Ki-67 reduction in SDG arm (OC & non-OC avg.)	Power
2.5%	0%	0%	1.7%	50%
2.5%	20%	0.5%	1.8%	55%
2.5%	50%	1.3%	2.1%	68%
2.5%	70%	1.8%	2.3%	76%
2.5%	100%	2.5%	2.5%	83%

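### The hormone comparison in 11.2 does not use the oral-contraceptive stratum the trial randomises by, and the 11.2 cycle-length sentence omits the restriction in objective 3

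*Combined protocol and SAP*

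**What the plan says.** **Hormones.** Section 11.2 states: "We will examine whether SDG has any effects on serum levels of bioavailable estradiol, and testosterone, determined at baseline and after 12 months". For the method it says "similar methods as above will be used to compare the treatment and control groups at two time points for all markers", naming serum hormones among these markers. The methods above are a two-sample t-test on change, analysis of covariance on the baseline value if the arms differ significantly at baseline, and a rank test if skewness is extreme. OC status appears in none of them. The regression paragraph concerns Ki-67 and does not list OC use among its example covariates. The correlative analyses name BMI, age and SNPs as modifying variables, again without OC use.

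**OC users.** Section 11.0 makes site and OC use the only stratification factors, and 4.6.3 implements the OC split through the study ID sequence. Section 11.1 says "we expect to recruit 72 women taking oral contraceptives (OC) and 148 women not taking OCs" and describes SDG's efficacy in OC users as unknown. Section 2.4.3 explains that the pilot left OC users out partly because "it might be more difficult to demonstrate biomarker modulation from SDG in the face of exogenous hormones".

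**Menstrual cycles.** Objective 3 in section 1.0 specifies "a menstrual diary for cyclicity and cycle length for women not on cycle modulating contraceptives". The analysis sentence in 11.2 reads "We will determine whether addition of SDG alters the frequency or length of menstrual cycles", with no such limit.

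**Cycle day.** Baseline hormone blood is taken at the RPFNA visit (6.2.4), and RPFNA must fall on day 1 to 10 of the cycle at baseline and at 12 months (6.1). Of AMH, 11.2 says "A distinct advantage for trial purposes is that it does not vary with day of menstrual cycle".

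**The concern.** Exogenous hormones bear more directly on estradiol and testosterone than on any other secondary endpoint. The protocol recognises the dilution problem for Ki-67: the table in 11.1 shows power falling from 83% to 50% as the assumed efficacy in OC users falls from 100% to zero. That reasoning is not carried into the hormone analyses. If the effect on hormones differs by OC use, a single overall difference averages two unlike effects. A null result could not then be read as no effect in women off OCs, and a positive one could not be read as applying to OC users.

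The cycle-length point is one of consistency. A programmer working from section 11 alone, where all analyses are declared intent-to-treat, would not find the restriction that objective 3 sets.

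**Working it through.** **Inputs.** From 11.1: 220 evaluable women, 2:1 allocation, 72 OC users and 148 non-users, effect 2.5 points, SD 6 points. From 11.2: two-sided 5%. The documents give no effect size, SD or power for the hormones, so the Ki-67 figures serve below as a stand-in on a standardised scale (2.5/6 = 0.417 SD).

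**1. The plan's own power figures.** Power ≈ Φ(δ/SE − 1.96), with SE = 6 × √(1/146.67 + 1/73.33) = 6 × 0.143 = 0.858. For δ = 2.5: 2.5/0.858 = 2.913, and Φ(0.953) = 83.0%, as stated. Let e be the effect in OC users relative to non-users. The average effect is 2.5 × [148/220 + e × 72/220].

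| e | Dilution (72/220)(1 − e) | Average, unrounded | Power, unrounded average | Power, printed average | Power stated |
|---|---|---|---|---|---|
| 0 | 32.7% | 1.682 | 50.0% | 50.8% | 50% |
| 0.2 | 26.2% | 1.845 | 57.6% | 55.5% | 55% |
| 0.5 | 16.4% | 2.091 | 68.3% | 68.7% | 68% |
| 0.7 | 9.8% | 2.255 | 74.8% | 76.4% | 76% |
| 1 | 0% | 2.500 | 83.0% | 83.0% | 83% |

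The stated powers reproduce from the printed averages. The gap in the 20% row is rounding.

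**2. Dilution for hormones.** The same fraction, (72/220)(1 − e), applies to any endpoint averaged over these women. It runs from 0% at e = 1 to 32.7% at e = 0. Nothing in the documents fixes e for estradiol or testosterone.

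**3. Would analysing only non-OC women be better?** With equal SDs, restriction multiplies the non-centrality by √(148/220) = 0.820. In the stand-in example this gives 2.913 × 0.820 = 2.390 and Φ(0.430) = 66.6%. Using all 220 women multiplies it by 1 − (72/220)(1 − e). The two are equal at e = 1 − (1 − 0.820) × 220/72 ≈ 0.45. Restriction gains power below that value and loses it above: at e = 0.7 it gives 66.6% against 74.8%.

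**4. Sensitivity to the equal-SD assumption.** If OC use holds these hormones steadier, the SD of change in OC users would be smaller. Taking half the SD as an assumption, with e = 0, the pooled variance falls by the factor (148 + 72 × 0.25)/220 = 0.755. The non-centrality is 2.913 × 0.673/√0.755 ≈ 2.256, and power is Φ(0.296) ≈ 62%, not 50%. Most of the gap to 66.6% closes.

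**5. Precision of within-stratum estimates.** With 2:1 allocation the SE in SD units is √(4.5/n): 0.143 for 220, 0.174 for 148 and 0.250 for 72. The interaction has SE √(0.174² + 0.250²) = 0.305, which is 2.13 times the overall SE. Even with 0.417 SD in non-users and nothing in OC users, its power is Φ(0.417/0.305 − 1.96) ≈ 28%.

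**6. Confounding.** OC use is stratified at randomisation, so the arms should be balanced on it. What is at issue is dilution and precision, not bias from imbalance.

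**7. Cycle endpoint, text against text.** Objective 3 defines the population and 11.2 does not mention it. Nothing in 11.2 says that women on cycle-modulating contraceptives are to be included. Read together, the sections exclude them and dilution by this route is zero. What remains is a missing cross-reference.

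**The case against.** OC users were admitted deliberately, to widen the application of the results (section 3.0), so an overall estimate is a legitimate target. Stratified randomisation keeps the comparison fair. The hormones are secondary endpoints tested without multiplicity control. All of this stands. It argues against replacing the overall estimate with a non-OC one, but not against using a stratum that is already known for every woman.

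Three stronger readings are tempting, and the documents do not support them:

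- **That cycle length is analysed with OC users pooled in, which tilts the result towards the hypothesised "no significant impact on menstrual cycle length".** Objective 3 already excludes women on cycle-modulating contraceptives, and 11.2 merely fails to repeat this. The 26% with irregular menses in the pilot (2.4.4.5) comes from a single-arm study and does not show an SDG effect.
- **That the plan ignores cycle day.** Hormone blood is tied to the day 1 to 10 RPFNA visit at both time points. The 12-month visit may move by up to two months to fit the cycle (6.5), and non-menstruating women need follicular phase confirmed by hormone levels (4.4.1). A secondary efficacy analysis is limited to women confirmed as follicular at both RPFNAs (11.2). Only variation within the window is left unadjusted. The remark about AMH suggests that this variation may matter but does not say how much.
- **That effects are diluted by a third.** This is the limiting case of no effect in OC users. The drop in power that goes with it also assumes equal SDs, which sits badly with the idea that OC use steadies these hormones (step 4).

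Nor are the 148 women off hormonal contraception. They are women not taking oral contraceptives; section 4.2.3 allows non-oral hormonal methods and 4.2.4 allows hormonal IUDs.

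**Conclusion.** The point holds for the hormones. Section 11.2 has no OC-stratified or OC-adjusted comparison of estradiol and testosterone, although OC use is a randomisation factor, about 33% of evaluable women are expected to be OC users, and the protocol itself gives the reason to expect a weaker signal in them. The possible dilution is 0% to 33%, depending on an unknown relative effect. This assumes the expected 72/148 split and, for the power figures, the Ki-67 effect size and SD as a stand-in. The arm comparison remains valid.

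For menstrual cycles, the finding is only that 11.2 should match objective 3. For cycle day, an adjustment within the sampling window is optional. The primary endpoint is not affected by any of this.

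**What to change.** In 11.2:

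1. Analyse change in bioavailable estradiol and testosterone with OC stratum in the model. Keep the overall stratum-adjusted estimate, and beside it report the SDG-placebo difference with confidence interval in each OC stratum (about 148 non-OC and 72 OC women) and a treatment-by-stratum interaction. Adjustment alone removes between-stratum variation; it does not undo dilution. The within-stratum estimates are what show whether dilution is present.
2. Add objective 3's restriction to the sentence on cycle frequency and length, and say which contraceptives count as cycle-modulating, since that group is not the same as the OC stratum. State also how women without periods after ablation or hysterectomy are handled.
3. Optionally, as a sensitivity analysis in menstruating women, adjust the hormones for cycle day at each draw within the day 1 to 10 window.

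The cost is SAP wording and a few model terms. OC status is known from randomisation, and cycle day should be recoverable from the RPFNA scheduling. The price is precision: with equal SDs the SE is 1.22 times the overall SE in non-OC women (√(220/148)) and 1.75 times in OC users (√(220/72)). The interaction test has low power, so a non-significant result should not be read as evidence that the effects are equal.
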